Design: This is an exploratory study to determine whether $[^{11}C]PBR28$ can detect the increased TSPO associated with neuroinflammation by scanning subjects who have shown MRI abnormalities in the acute phase. We also investigate whether [¹¹C]PBR28 detects changes in the chronic phase as recently reported using an old ligand, [¹¹C]PK 11195. Two groups of TBI subjects will be studied depending on their availability relative to the time of injury. To investigate changes in TSPO in the areas of MRI abnormalities in the acute phase, one group of TBI subjects (n = 20) will be studied who have shown TBI- related MRI abnormalities. These participants will have up to four [¹¹C]PBR28 PET scans; one to two PET scans within approximately 10 days of head injury, a third PET scan approximately three months after injury, and a fourth scan approximately one year after the scan at ~three months. To study changes in TSPO in the chronic phase, another group of TBI subjects will be enrolled who had brain injury more than ~5 months but within 5 years ago and meet the criteria of TBI by CNRM. This separate group is included because some TBI subjects are being recruited by CNRM only sometime after the injury. The participants at the chronic phase will have one PET and one MRI scan. In addition to MRI data, for all TBI subjects, clinical information obtained in 10-N-N122 (only the acute phase) and 11-N-0084 (both acute and chronic phase) will be used to evaluate the utility of the PET data in order to better understand the pathology of TBI. If the TBI subject is recruited from another protocol under CNRM, the clinical information obtained under the CNRM protocol will be used for 12-M-0063 as long as both the CNRM protocol and the TBI subject allow.

Outcome Measures: In this exploratory study to investigate the ability of [¹¹C]PBR28 PET to detect increases in TSPO, the primary goal will be to measure the magnitude and variance of any

increases observed in [¹¹C]PBR28 binding in areas of inflammation following TBI. Those data may be used to design future studies with a larger sample size.

4. Introduction/ Scientific Rationale

Traumatic brain injury

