For all subjects including TBI subjects who have PET scans within ~10 days and whose results on the affinity status will be available after the PET scans within ~10 days, the results of the affinity status will be used for post hoc analysis of the results. Such analyses are useful because as stated above, PET data itself does not differentiate high- and low-affinity binders. Only low affinity binders are clearly identified by PET.

5. Study objectives or hypotheses

This exploratory study aims to investigate the utility of PET TSPO imaging in TBI. Based on the literature and the preliminary results of protocol 10-N-N122 and literature reviewed above, we hypothesize that PET [¹¹C]PBR28 imaging in TBI patients will show increased TSPO in the areas of brain injury due to inflammatory reactions. Pilot data obtained via the current study are needed to estimate the prevalence of PET positive imaging in subjects with TBI, in order to help design future hypothesis-driven studies with a larger sample size based on proper power calculations. Relationship between PBR28 binding and neurocognitive function will also be studied to obtain pilot data to design future studies. We will also attempt to compare the time course of the changes in PET and MRI and changes in TSPO in the chronic phase of TBI.

6. Subjects

a. Study populations

The following three groups will be studied.

Group 1 (n = 20): Subjects with a history of acute head injury and MRI scans showing TBI-related changes.

Group 2 (n = 20): Subject who had brain injury \sim 5 months – 5 years ago and meet criteria of TBI established by CNRM.

Group 3 (n = 20): Age-matched healthy controls

b. Inclusion criteria

Subjects with TBI:

Subjects with TBI eligible for participation in this research study must meet the following inclusion criteria. Depending on the timing of the availability of the subjects the following two groups will be studied. No subject will be enrolled in both group 1 and 2.

Group 1 Acute/subacute phase (n = 20)

- 1. Diagnosis of non-penetrating TBI caused by a head injury within ~5 months.
- 2. Ambulatory.
- 3. Able to provide self consent without a legally-authorized representative based on the assessment of the Decision Making Capacity (DMC) by the Human Subjects Protection Unit (HSPU).

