For both TBI subjects and healthy subjects, screening assessments will include a diagnostic interview, neurological assessment, physical examination, lab work (Complete Blood Count (CBC), Complete Metabolic Panel (CMP), and urine analysis, urine toxicology screen). Screening will be done in the outpatient clinic/Day Hospital and will include a nursing assessment. For subjects with TBI, written consent will be obtained to use as much of this information as possible from protocol 10-N-N122 or from the CNRM. Some healthy subjects will be evaluated under the general screening protocol 01-M-0254. Screening procedures will not be repeated for healthy subjects if performed under the screening protocol within 12 months for diagnostic interview, neurological assessment, and physical examination, or six months for blood and urine tests. Otherwise, tests will be conducted as part of this study. Subjects will be screened for MRI safety using the screening questionnaire used by the Radiology and Imaging Sciences Program of the Clinical Center (Appendix 3).

iv. Study design

Group 1 (TBI in acute/subacute phase): This group will have [¹¹C]PBR28 PET scans at up to four time points. We will attempt to perform two of these scans within approximately 10 days of head injury as long as they are willing to do two and the scheduling allows. Two PET scans will be attempted on all TBI subjects, both occurring within ~10 days of injury. While every effort will be made to obtain both scans, completion of the imaging assessment may not be possible due to limited availability of the scanner, off-hours staffing, and other key resources. The target time for the first PET scan will be 1-5 days following head injury. The target time for the second PET scan will be 6-10 days. The minimal interval between two scans is 2 days, and the maximal interval is 7 days. If the TBI subjects are not willing to have two [¹¹C]PBR28 scans or schedule does not allow, one PET scan will be performed. In addition, one PET scan will be conducted at approximately 90 days after injury (90 +/- 50 days) and the last PET scan will be conducted approximately one year (but not within one year) after the previous scan and within 5 years of injury. MRI scans at each time point will be performed under the current protocol or 10-N-N122. Clinical information will be obtained through protocol 10-N-N122 or CNRM. The end point of study enrollment is 5 years from brain injury.

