The primary outcome measure will be the binding levels of [¹¹C]PBR28 measured as total distribution volume V_T and V_T normalized to plasma free fraction (f_P), V_T / f_P using dynamic brain data and metabolite-corrected arterial input function. Secondary outcome measures will include neuropsychology test scores obtained by the tests described in section 7. Study Design and Mehtods. A. Study phases. V. Study procedures. Neuropsychology tests. V_T and V_T / f_P in the areas of MRI abnormalities in TBI subjects will be compared to those in the areas without MRI abnormalities in the same subject and V_T and V_T / f_P in healthy controls. In TBI subjects, relationship between V_T or V_T / f_P and neuropsychology test scores will also be studied.

11. Statistical analysis

a. Analysis of data / study outcomes

Data obtained from TBI subjects who have a [¹¹C]PBR28 brain within approximately 10 days of head injury and are identified as low-affinity binders will be excluded based on the fast decline of brain activity (Kreisl *et al.*, 2010). Healthy controls identified as low affinity binders will be excluded before their [¹¹C]PBR28 brain scan.

Group 1 of TBI - Acute/subacute phase:

The main analysis will be performed to study whether [¹¹C]PBR28 PET shows changes in TSPO in areas where radiologist(s) report changes in MRI.

[¹¹C]PBR28 binding will be measured as V_T and V_T / f_P using dynamic brain data and metabolite-corrected arterial input function. These distribution volumes will be calculated in each voxel using the Logan plot and may also be calculated by other commonly used methods such as compartmental modeling and spectral analyses. In addition, to calculate distribution volumes from less noisy data, volumes of interest may be placed in individual PET images of the dynamic data and distribution volumes may be calculated by commonly used methods of quantification such as compartmental modeling and the Logan plot. V_T and V_T / f_P in the areas of abnormal MRI findings will be compared with those on the contralateral side of the same subject if the MRI is normal on the contralateral side. In addition, V_T and V_T / f_P in the areas of abnormal MRI findings will be compared with those of healthy controls.

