In addition to studying [¹¹C]PBR28 binding in the areas with abnormal MRI findings, V_T and V_T / f_P of [¹¹C]PBR28 of TBI subjects in areas with normal MRI findings will be compared to those of healthy controls. HIV infection and usage of drugs of abuse may be a confounding factor in this comparison because HIV infection was reported to increase TSPO (Cosenza-Nashat *et al.*, 2009) and drugs of abuse may cause neuroinflammation (Yamamoto *et al.*, 2010). Therefore, the results of HIV tests, urine drug screen, and history of using drugs of abuse may help interpretation of the PET results.

Group 2 of TBI - Chronic phase:

[¹¹C]PBR28 binding measured as V_T and V_T / f_P will be compared between the site of injury and the contralateral side if it showed no structural changes at the time of injury and at the time of PET. In addition, PBR28 binding in all brain areas will be compared with that in healthy controls because a recent study using the old ligand [¹¹C]PK 11195 showed increase in TSPO in certain brain regions irrespective of the site of brain injury (Ramlackhansingh *et al.*, 2011). As stated above for Group 1, the results of HIV tests, urine drug screen, and history of using drugs of abuse may help interpretation of the PET results.

For both Groups 1 and 2:

As an exploratory analysis, we will also study the relationship between $V_{\rm T}$ and $V_{\rm T} / f_{\rm P}$ of [¹¹C]PBR28 in TBI subjects in conjunction with their neuropsychology test scores.

In addition to the quantitative analysis based on V_T and V_T / f_P values, [¹¹C]PBR28 parametric images may be visually evaluated by study investigator(s) blind to subject's diagnosis, in order to inform future use in clinical settings. As an exploratory analysis, correlation between [¹¹C]PBR28 binding and neuropsychological test scores will be studied.

b. Criteria for significance, power analysis, and accrual number request

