In this exploratory study to investigate the ability of [¹¹C]PBR28 PET to detect increases in TSPO, the primary goal is to measure the magnitude and variance of putative increases in [¹¹C]PBR28 binding in inflammatory areas in TBI subjects. Those data may be used to design future studies with a larger sample size. If [¹¹C]PBR28 binding is indeed increased in TBI subjects, statistical significance will be tested by comparing binding on the contralateral side in the same subject if the contralateral side shows normal MRI results, and also by comparing binding in healthy controls. The association between [¹¹C]PBR28 binding and clinical scores obtained from the neuropsychological test scores may also be used to design future studies with a larger sample size. The statistical significance of regression in the current study will also be assessed.

Because of the exploratory nature of the current protocol, we request a relatively small sample size of 20 in each group. After taking into account dropouts, we expect to perform at least one [¹¹C]PBR28 PET scan in approximately 15 subjects in each group. A pilot study of this sample size is usually adequate for studying the utility of PET brain molecular imaging and calculating the necessary sample size of future studies.

12. Human Subjects Protection

a. Subject selection

The racial and ethnic distribution of the subjects will reflect those of the clinical population affected by TBI and the participating hospital. No gender or ethnic/racial background preference or exclusion will apply to subject recruitment. We anticipate that approximately 60% of the subjects will be male.

b. Justification for inclusion / exclusion of children

Because the study involves radiation exposure, children will be excluded.

c. Justification for inclusion of other vulnerable subjects

Written informed consent will not be waived for this study. We will include TBI subjects who signed a consent form for protocols 10-N-N122, 11-N-0084 or other CNRM protocols for him/herself without requiring a legally-authorized representative. Pregnant or breast feeding women will be excluded because of the radiation exposure from [¹¹C]PBR28.

Procedures for consent are described in Section 15.

d. Justification of sensitive procedures (use of placebo, medication withdrawal, provocative testing)

None of these sensitive procedures apply to this protocol.

e. Safeguards for vulnerable populations

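### Does the plan need a rule for PET-positive scans because Section 5 mentions their prevalence?

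*Combined protocol and SAP*

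**What the plan says.** Section 5 sets out a directional hypothesis, that TBI patients will show raised TSPO in injured areas, and adds: "Pilot data obtained via the current study are needed to estimate the prevalence of PET positive imaging in subjects with TBI". The purpose given is help with designing and powering later studies.

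The rest of the plan works with continuous binding. The Outcome Measures paragraph of the précis says "the primary goal will be to measure the magnitude and variance of any" increases observed, and Section 11.b repeats that goal. Section 10 makes V_T and V_T/f_P the primary outcome. In Section 11.a, the main Group 1 analysis asks whether "PET shows changes in TSPO in areas where radiologist(s) report changes in MRI". For Group 2, binding "will be compared between the site of injury and the contralateral side if it showed no structural changes at the time of injury"; the same condition applies when the PET scan is done. The nearest thing to a positive or negative reading is in Section 11.a for both groups: "parametric images may be visually evaluated by study investigator(s) blind to" diagnosis. That reading is optional and has no call criterion.

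Section 7.a.iv gives Group 1 "PET scans at up to four time points" and Group 2 one scan. On numbers, Section 11.b requests 20 per group and says "After taking into account dropouts, we expect to perform at least one" PET scan in about 15 of them. It also says that if "binding is indeed increased in TBI subjects, statistical significance will be tested by comparing binding on the contralateral side in the same subject" where that side is normal on MRI, and against healthy controls.

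**The concern.** A prevalence needs three things: a rule that makes a subject positive, a scan to apply it to, and a planned proportion. The plan supplies none of them. Group 2 has only one scan, but in Group 1 the choice is open. Subjects have between one and four scans, some may join only at about three months, and Section 4 says the best time to image inflammation with PET is unknown. If someone later reported a prevalence, the cut-off and the scan could be picked after seeing the data, and the confidence interval would not show that freedom. Later studies might then be powered on a flattering figure.

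The wording on direction raises a second worry. The précis and Section 11.b speak of increases, and Section 11.b makes testing conditional on one, whereas Section 11.a plans its comparisons without that condition. If only increases were summarised, their size would be overstated and their variance understated.

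**Working it through.** **Plan's own figures.** 20 per group with about 15 scanned implies a loss of 1 − 15/20 = 25%. The plan gives no alpha, power, SD, effect size or expected prevalence. The 20 is justified by the exploratory aim alone, so no sample-size argument depends on a prevalence.

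**Does any planned result use a positivity call?** Going through Sections 10, 11.a and 11.b: the primary outcome, the lesion-versus-contralateral comparison, the comparison with controls and the regression on neuropsychology scores all use V_T or V_T/f_P directly. None needs a subject to be classified.

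**Precision of a prevalence if one were reported.** Exact (Clopper-Pearson) 95% limits for x of n are the 0.025 quantile of Beta(x, n − x + 1) and the 0.975 quantile of Beta(x + 1, n − x).

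- 7/15: 0.213 to 0.734, a width of 52 percentage points
- 10/20: 0.272 to 0.728
- 5/10 (if only 10 are assessable): 0.187 to 0.813

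**Effect of the cut-off.** The documents give no SDs, so these are assumptions: lesion-to-contralateral log-ratio with mean 0.10 and SD 0.12; controls' left-right SD s = 0.06, range 0.04 to 0.08. With the cut-off c control SDs above a control mean of zero, the proportion positive is 1 − Φ((c·s − 0.10)/0.12).

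| c | s = 0.04 | s = 0.06 | s = 0.08 |
|---|---|---|---|
| 1 | 69% | 63% | 57% |
| 2 | 57% | 43% | 31% |
| 3 | 43% | 25% | 12% |

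At s = 0.06 the span is 63 − 25 = 38 points. At s = 0.08 it is 57 − 12 = 45 points from the rounded values. Both are narrower than the 52-point interval for 7/15.

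**Effect of the scan.** Take the one-sided 95% prediction limit from 15 controls: t(0.95, 14) × √(16/15) = 1.761 × 1.033 = 1.819 control SDs, which is 1.819 × 0.06 = 0.109 on the log-ratio scale. One named scan gives 1 − Φ((0.109 − 0.10)/0.12) = 47%. Counting a subject as positive if any scan is positive, with between-scan correlation 0.8 to 0.5, gives:

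- four scans, mean 0.10 at each: 66% to 77%
- two scans, mean 0.10 at each: 57% to 64%
- four scans, means 0.10, 0.10, 0.05 and 0: 59% to 69%

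The first line assumes that every subject completes all four scans and that the signal never fades, so it is an upper-end case.

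**Would a control-based rule settle the matter?** With the same limit and a mean lesion change of zero, the proportion positive is 1 − Φ(0.109/0.12) = 1 − Φ(0.91) = 18%. A nominal 5% rule would therefore call 18% positive with no average change, because lesion ratios are assumed to vary more than control ratios.

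**Testing only after an increase.** With true mean 0.10 and n = 15, the standard error is e = SD/√15. The expected mean given that it exceeds zero is 0.10 + e·φ(0.10/e)/Φ(0.10/e). For SDs of 0.10, 0.12, 0.15 and 0.20 this is 0.1000, 0.1001, 0.1006 and 0.1032. Group-level conditioning therefore adds at most 0.3 of a percentage point here. Dropping individual subjects without an increase would be another matter: at SD 0.12, 0.10 + 0.12·φ(0.833)/Φ(0.833) = 0.142. Nothing in Section 11.a instructs that. Its comparisons are defined by where the MRI is abnormal and whether the contralateral side is normal, not by the sign of the PET result.

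**The case for a change.** The best case for a change is that Section 5 gives prevalence as a reason the pilot is needed, and a study should either deliver a stated purpose or not state it. Being exploratory does not answer that. The freedom over cut-off and scan is large under any plausible assumptions, no scan is the obvious default, and the interval attached to a later prevalence would hide the choice. Deleting the clause or adding a short rule would cost almost nothing.

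The factual part stands: the aim and the analysis do not meet on this point, and a prevalence produced after the data are seen should not be read as prespecified. The need for a change does not follow. Deletion alters no result. A rule brings in a choice that is itself open to dispute: the control-based limit above calls 18% positive with no mean change, misses bilateral increases, and pools high- and mixed-affinity binders, although Section 4 foresees post hoc use of affinity status. The continuous values are kept in any case, so an analyst who wants a proportion can fix a rule and a scan window before computing it.

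On direction, the text could be tidier, but the increase wording follows the hypothesis in Section 5, and Section 11.a already sets out the comparisons without a condition on sign.

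**Conclusion.** No change is called for. This is missing detail on a planning remark, and analysts can fill it sensibly. The primary goal, magnitude and variance of binding, is met by the continuous outcomes, and following the plan as written gives sound results. A prevalence from about 15 subjects would be too imprecise to guide a later design (21% to 73% for 7/15), with or without a rule fixed in advance. The cut-off and scan effects are real but rest wholly on assumed means, SDs and correlations. The wording on increases adds negligible bias at group level (10.0% to 10.3% against a true 10%, at n = 15 and SD 10% to 20%), provided that all evaluable subjects are kept whatever the sign of their change, which is the natural reading of Section 11.a.

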- 7. Exposure to research related radiation in the past year that, when combined with this study, would place subjects above the allowable limits.

Healthy subjects are not eligible for participation in this research study if any of the following conditions exist:

- 1. Any past or present history of DSM Axis I disorder, with the exception of substance abuse that ended over 6 months prior to enrollment.
- 2. Contraindication to MRI scanning including certain metal implants or devices such as: cardiac pacemaker, insulin infusion pump, implanted drug infusion device, cochlear, otologic, or ear implant, transdermal medication patch (Nitroglycerine) that cannot be removed for the study, body piercing(s), bone/joint pin, screw, nail, plate, wire sutures or surgical staples, shunts, cerebral aneurysms clips, shrapnel or other metal imbedded in a subject's body (such as from war wounds or accidents or previous work in metal fields or machines that may have left any metallic fragments in or near the subject's eyes).
- 3. Conditions precluding entry into the scanners (e.g. morbid obesity, claustrophobia, etc.).
- 4. In female subjects, pregnancy or breastfeeding.

- 5. Clinically significant laboratory abnormalities, as defined as laboratory values that are out of normal range or require clinical workup and/or treatment.
- 6. Exposure to research related radiation in the past year that, when combined with this study, would place subjects above the allowable limits.
- 7. Previously determined as a low-affinity binder in another study on TSPO
- 8. Positive results of urine drug screen on enrollment.

HIV positive subjects are considered healthy as long as he / she does not show neurological or psychiatric symptoms based on history and physical exams. Results of HIV test in both TBI subjects and healthy controls may help interpretation of the PET results (see section 11. Statistical analysis. a. Analysis of data / study outcomes). Results of urine drug screen and history of using drugs of abuse may also help interpretation of the PET results. In addition, inclusion of TBI subjects who show positive for urine drug screen may improve recruitment of TBI subjects.

d. Eligibility Checklist

Eligibility checklist is attached as Appendix 1.

7. Study Design and Methods

a. Study phases

i. Study overview

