One antecubital venous and one radial arterial catheter will be placed. The venous catheter is for radioligand injection and the arterial catheter is for blood sampling. An anesthesiologist or credentialed staff in the Vascular Access Department will place the arterial catheter in the subject's wrist after numbing the area with a local anesthetic to minimize discomfort.

The subject will then undergo scanning in a PET, PET/CT, or PET/MRI camera located at the Clinical Center of NIH. The subject will be placed on the scanner bed with his/her head held firmly in place with a thermoplastic mask fixed to the bed. An initial transmission scan for PET, or a pre-emission CT for PET/CT camera will provide a measured attenuation correction. The PET/MRI camera does not require a transmission scan using radioactivity because attenuation is measured by an MRI scan. The radioligand (~10 - 20 mCi of [¹¹C]PBR28) will be injected intravenously. The maximum allowed mass of the radiotracer will be 10 µg per injection. The scan will last approximately 2 - 2.5 hours with an additional ~ 2 - 2.5 hours for preparations such as catheter insertion.

To measure input function of the radioligand, blood samples will be obtained manually from the arterial line. The total blood sampling volume during the scan will be no more than 100 mL.

Pulse, blood pressure, and respiratory rate will be recorded within 3 h before tracer injection, and again at about 15, 30, 90, and 120 min after tracer injection. Before discharge, the

arterial and venous catheters will be removed and catheter sites will be assessed for any evidence of vascular changes or trauma prior to releasing the subject from the NIH. Participants will be monitored during the PET procedure for the development of excessive anxiety and any adverse effect.

If the PET scan is cancelled or incomplete due to synthesis failure of [¹¹C]PBR28 or to camera problems and the subject did not receive any radioactive material, the scan will be repeated on the same or on another day. The transmission scan may be repeated as well.

MRI scan:

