Data sharing will be governed by standard data transfer agreements and approved by the CNRM and NIH ethics committees. Data used outside of NIH as part of collaborations will be anonymized, although non-identifying demographic data (e.g., height, age, race) may be provided. Participants will be informed of the possibility of data sharing during the informed consent process.

8. Risks/ discomforts

Risks of study participation and minimization of risks

Potential risks and discomforts from this study include those associated with: i) medical examinations including laboratory testing, ii) radiation exposure risks, iii) PET scanning, iv) placement of arterial and venous lines, v) blood sampling, vi) MRI, and vii) cognitive testing.

i) Medical Examination and Laboratory Testing

No medical risks are associated with taking of medical history, physical examination, or laboratory tests other than risks from phlebotomy. Phlebotomy may lead to the formation of small subcutaneous hematomas caused by blood leaking from a punctured blood vessel. These hematomas typically cause only minor discomfort. There is also a small risk of infection at the site of the needle puncture, which can be readily treated with antibiotic therapy.

ii) Radiation Exposure Risks

Radiation exposure in this protocol will be from up to four [¹¹C]PBR28 scans and four transmission scans for TBI subjects and one [¹¹C]PBR28 and one transmission scan for healthy controls. The radiation absorbed dose for the transmission scans will depend on the scanner used. The effective dose of one transmission scan from a PET camera using a ⁶⁸Ge source is 0.01 rem; for cameras using a ¹³⁷Cs source, the dose is 0.0003 rem. The effective dose of one transmission scan for head from a PET/CT camera that uses CT for transmission is 0.6 rem. Based on data obtained from whole body imaging of healthy humans performed at the Molecular Imaging Branch (MIB) (Brown *et al.*, 2007), we estimate that the highest effective dose calculated for humans from the current study who have three [¹¹C]PBR28 scans using PET-CT is 1.65 rem within one year, which is well below NIH RSC annual guidelines of 5 rem. Some TBI subjects have one or two [¹¹C]PBR28 scans within one year and will have lower levels of radiation

exposure. Radiation Safety Committee requires us to report radiation exposure within a year, and no TBI subject will have four PET scans within one year.

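### The stated one-year maximum dose for three PET-CT scans (1.65 rem) is less than the dose from their three CT transmission scans alone (1.80 rem)

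*Combined protocol and SAP*

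**What the plan says.** Section 8, ii) Radiation Exposure Risks, gives the component and the total in consecutive sentences. The component: "The effective dose of one transmission scan for head from a PET/CT camera that uses CT for transmission is 0.6 rem". The total, for a subject with three radioligand scans in a year: "scans using PET-CT is 1.65 rem within one year, which is well below NIH RSC annual guidelines of 5 rem". The same paragraph gives much smaller transmission doses for cameras that use a radioactive source: 0.01 rem (⁶⁸Ge) and 0.0003 rem (¹³⁷Cs).

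Transmission scans are paired one-to-one with PET scans. Section 8 counts up to four radioligand "scans and four transmission scans for TBI subjects and one" of each for healthy controls. Section 7.a.v (PET scan procedure) says: "An initial transmission scan for PET, or a pre-emission CT for PET/CT camera will provide a measured attenuation correction". It adds, for a scan cancelled or incomplete before any radioactivity is given: "The transmission scan may be repeated as well".

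The injected activity is given as a range, "The radioligand (~10 - 20 mCi of" the tracer, with no conversion to effective dose.

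The total bears on eligibility. Section 6.c excludes a subject with "Exposure to research related radiation in the past year that, when combined with this study, would place subjects above the allowable limits", and Section 8 sets that limit at 5 rem per 12 months.

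**The concern.** A stated maximum should be at least the sum of its listed parts. Here one part, the CT, exceeds the whole. Either the CT entry is too high, or the 1.65 rem figure understates the total or leaves part of it out.

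Which of these is true matters, because 1.65 rem is the only study total in the documents available. It supports the statement that exposure is far below the annual guideline. It is also the natural number to add to prior research exposure when applying the exclusion criterion. If it is too low and staff use it that way, a Group 1 subject with substantial exposure in the previous year could be accepted above the limit. If the CT entry is wrong instead, only the risk text needs correcting.

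**Working it through.** **Inputs**

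- CT transmission dose, PET/CT camera: 0.6 rem per scan (Section 8.ii).
- Stated one-year maximum, three scans on PET-CT: 1.65 rem (Section 8.ii).
- Transmission scans per PET scan: one (Sections 7.a.v and 8.ii).
- Most PET scans in one year: three. Section 7.a.iv allows two within about 10 days of injury, then "one PET scan will be conducted at approximately 90 days after injury (90 +/- 50 days"), with the last scan more than a year after that. Section 8.ii confirms that nobody has four in a year.
- Limit: 5 rem per 12 months (Section 8.ii).
- Tracer dose per injection, *d*: not in the documents available.

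**Trying to reproduce 1.65 rem**

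Total = 3 × (transmission dose + *d*).

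- CT part: 3 × 0.6 = 1.80 rem.
- Left for tracer: 1.65 − 1.80 = −0.15 rem, or −0.05 rem per injection. This is impossible.
- Per session: 1.65 / 3 = 0.55 rem, which is 0.05 rem less than one CT. For 1.65 rem to be a full total, the CT dose must be below 0.55 rem.

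The stated figure cannot be reproduced with the stated CT dose. With the ⁶⁸Ge source it would imply (1.65 − 0.03) / 3 = 0.54 rem per injection, which is possible, but the sentence describes PET-CT.

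**Ways it could resolve**

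| Reading | One-year total (rem) | Left under 5 rem |
|---|---|---|
| A. 1.65 is right, CT entry is wrong | 1.65 | 3.35 |
| B. 0.6 is right, 1.65 is tracer only | 1.80 + 1.65 = 3.45 | 1.55 |
| C. 0.6 is right, total mis-summed | 3 × (0.6 + *d*) | 5 − 3 × (0.6 + *d*) |

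- Under A, if 0.6 were a decimal slip for 0.06 (an assumption), *d* = (1.65 − 3 × 0.06) / 3 = 0.49 rem.
- Under C, with *d* assumed at 0.2, 0.3, 0.4 and 0.5 rem, the total is 2.4, 2.7, 3.0 and 3.3 rem, leaving 2.6, 2.3, 2.0 and 1.7 rem. The documents give no basis for this range. Their only bound is a total above 1.80 rem.

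**When the 5 rem limit would be at risk**

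- Study dose alone: 3 × (0.6 + *d*) > 5 needs *d* > (5 − 1.80) / 3 = 1.07 rem per injection, or 1.07 / 20 = 0.053 rem per mCi at 20 mCi.
- With prior exposure: if 1.65 rem is added in the check but B or C is true, wrongful acceptance needs prior-year exposure between the true remainder (1.55 to 2.6 rem on these assumptions) and 3.35 rem.
- A repeated CT transmission scan would add a further 0.6 rem, which is not visible in the stated maximum.

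**The case against.** The mismatch has no good answer, but its importance can be disputed.

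- **The safety conclusion survives.** Readings A and B, and C over the assumed range, all stay under 5 rem. This stands. At worst, the claim of a wide margin becomes a claim of a smaller one.
- **Harm needs several conditions together.** The 0.6 rem figure must be the right one, staff must add 1.65 rem, and all three scans must be on PET/CT although PET and PET/MRI cameras are allowed. The subject must also complete both early scans, which Section 7.a.iv says may not be possible, and must have prior exposure in a particular band. This also stands. The protocol does not say that 1.65 rem is the number added, and it notes that annual exposure is reported to the Radiation Safety Committee.
- **It may be a labelling or decimal slip.** The 1.65 rem sentence rests on whole-body imaging of the radioligand, so a tracer-only reading is possible, although its reference to PET-CT points the other way. A slip for 0.06 rem is also possible. Either way, one figure is wrong or incomplete.
- **A dose per injection may appear elsewhere.** Consent pages are not among the documents available, and the cited dosimetry study is not at hand. This is fair, and the absence is not counted as a separate defect. Such a figure could show which entry is wrong, but could not make 1.65 rem a total that contains 1.80 rem of CT.

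**Conclusion.** The concern holds. The 0.6 rem and 1.65 rem figures cannot both be right as component and total: CT alone exceeds the total by 0.15 rem. This rests only on figures in Section 8 and on one transmission scan per PET scan, which the protocol states.

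The documents do not settle which figure is wrong, or which activity between 10 and 20 mCi the stated maximum assumes. The room left under the annual limit is therefore 3.35 rem if the total is right, and 1.55 rem if 1.65 rem is tracer only. The values between depend on an assumed tracer dose.

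The practical effect is modest. The three-scan case arises only in Group 1 (n = 20), since Groups 2 and 3 have at most one scan. Nothing shows that the study alone would pass 5 rem. It should still be corrected, because the figure supports a safety comparison and bears on an exclusion criterion.

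**What to change.** Check both figures against the dosimetry source. In Section 8.ii, state the effective dose per injection at the 20 mCi maximum and the dose per transmission scan for each camera type. Give the one-year maximum as the visible sum of these, and correct whichever entry is wrong.

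Use the corrected total in the 5 rem per 12 months check. Add the CT dose (0.6 rem or its corrected value) for any repeat CT transmission scan actually performed.

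The cost is a recalculation and a wording amendment to the risk section. The stated maximum may become less favourable. Design, endpoints and sample size do not change.
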